8.4.2. Conditions that should not be reported as serious adverse events

The conditions listed below, that may require hospitalization of a patient, are not considered to be SAE, and shall not be reported as such, but only need to be recorded in the CRF:

- Hospitalizations planned before entry into the clinical study which is part of the normal treatment or monitoring of the studied indication and not associated with any deterioration in condition.
- Hospitalization for routine treatment or monitoring of the studied indication, not associated with any deterioration in condition.
- Hospitalization for treatments, which was elective or pre-planned, for a pre-existing condition that is unrelated to the indication under study and did not worsen.
- Hospitalization for general care not associated with any deterioration in condition.
- Treatment on an emergency, outpatient basis for an event not fulfilling any of the definitions of SAEs given above and not resulting in hospital admission.

In addition, the following situation shall not be considered SAE:

- Trial end points
- Abnormal lab values or test results that do not induce clinical signs and/or symptoms and require intervention/therapy, i.e. are clinically significant.

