7. ENDPOINTS

7.1. STUDY ENDPOINTS

7.1.1. Efficacy endpoints

- 1. Percentage of patients who experience epithelial healing at 4 and 8 weeks. (Epithelial healing is defined as Grade 1 or absence of staining (Grade 0) in a previously qualifying zone.)
- 2. Percentage of patients who remain healed (as defined in #1 above) throughout the follow-up period.
- 3. Schirmer I change from baseline to weeks 4 & 8
- **4.** TFBUT change from baseline to weeks 4 & 8
- 5. Percentage of patients that achieve an improvement in corneal sensitivity in the NEI zone used to qualify in the study eye as measured by the Cochet-Bonnet aesthesiometer at 4 and 8 weeks, and at the last visit (week 32).
- **6.** Quality of life questionnaires change from baseline at week 8 and week 32
- 7. IDEEL
- **8.** EQ-5D-5L
- **9.** Mean change in BCDVA from baseline to Week 8.
- **10.** Percentage of patients that achieve a 15- letter gain in BCDVA at 4 and 8 weeks.

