7.1.3. Safety endpoints

1. Adverse Events (AEs) and Treatment-emergent adverse events (TEAEs), assessed throughout the study

EVALUATION OF ADVERSE EVENTS AND SAFETY INFORMATION

8.1. **DEFINITIONS**

Adverse Event

An **Adverse Event** (**AE**) is defined as any untoward medical occurrence in a patient or clinical investigation subject administered a pharmaceutical product and which does not necessarily have a causal relationship with this treatment. An AE can therefore be any unfavorable and unintended sign (including an abnormal laboratory finding), symptom, or disease temporally associated with the use of a pharmaceutical product, whether or not considered related to the Study Product.

This definition includes an exacerbation of preexisting medical conditions or events, historical conditions not present prior to study treatment, which reappear following study treatment, intercurrent illnesses, hypersensitivity reactions, drug-drug or drug-food interactions, medication errors, overdose (both intentional or unintentional), drug misuse/abuse, false positive laboratory test, or the significant worsening of the disease under investigation.

Adverse Drug Reaction

An **Adverse Drug Reaction (ADR)** is defined as an adverse experience which is reasonably likely to have been caused by the drug. An adverse reaction, in contrast to an adverse event, is characterized by the fact that a causal relationship between a pharmaceutical product and an occurrence is suspected. Medical judgment should be used to determine the relationship, considering all relevant factors, including pattern of reaction, temporal relationship, de-challenge or re-challenge, confounding factors such as concomitant medication, concomitant diseases, and relevant history.

Adverse drug reactions may arise from use of the Study Product within or outside the terms of the marketing authorization or from occupational exposure. Conditions of use outside the marketing authorization include off-label use, overdose, misuse, abuse, and medication errors, occupational exposure.

The Investigator carefully assesses relationship between event and Study drug using the information below

Arguments that may suggest a reasonable causal relationship could be:

- The event is consistent with the known pharmacology of the drug
- The event is known to be caused by or attributed to the drug
- A plausible time to onset of the event relative to the time of drug exposure

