- Evidence that the event is reproducible when the drug is re-introduced
- No medically sound alternative etiologies that could explain the event (e.g. pre-existing or concomitant diseases, or co-medications)
- The event is typically drug-related and infrequent in the general population not exposed to the drug
- An indication of dose-response (i.e. greater effect size if the dose is increased, smaller effect size if dose is diminished)

Arguments that may suggest that there is no reasonable possibility of a causal relationship could be:

- No plausible time to onset of the event relative to the time of drug exposure is evident (e.g. pretreatment cases, diagnosis of cancer or chronic disease within days/weeks of drug administration; an allergic reaction weeks after discontinuation of the drug concerned)
- Continuation of the event despite the withdrawal of the medication, considering the pharmacological properties of the compound (e.g. after 5 half-lives). Of note, this criterion may not be applicable to events whose time course is prolonged despite removing the original trigger.
- Additional arguments amongst those stated before, like alternative explanation (e.g. situations where other drugs or underlying diseases appear to provide a more likely explanation for the observed event than the drug concerned)
- Disappearance of the event even though the study drug treatment continues or remains unchanged.

Adverse events are to be considered unrelated if the relationship to the study drug as described in the table in section [8.3.2] is none or unlikely; whereas any AE reported in the study having a possible, probable or highly probable relationship to study drug will be considered as an ADR. [For the purposes of safety reporting, "reasonable possibility" means there are facts (evidence) or arguments to suggest a causal relationship between the drug and the adverse event.]

Adverse Event of Special Interest (AESI)

The term AESI relates to any specific AE that has been identified at the project level as being of particular concern for prospective safety monitoring and safety assessment within the study, e.g. the potential for AEs based on knowledge from other compounds in the same class.

In the present study, the following sight-threatening events will follow into the definition of AESI and will be considered equivalent to a SAE and will be reported following the procedures described below for the reporting of a SAE:

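### Protocol 8.4.2 excludes trial end points from SAE status without limit, in conflict with the sight-threatening-event rule and the SAE definition in 8.1

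*Protocol*

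**What the plan says.** Protocol 8.4.2 has two lists of things that are not SAEs. The first covers kinds of hospitalization and emergency outpatient care. Most of its items carry a limit, such as no deterioration in the patient's condition, or no SAE definition being met. The second list opens with "In addition, the following situation shall not be considered SAE" and has two items:

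- "Trial end points", with nothing further.
- "Abnormal lab values or test results that do not induce clinical signs and/or symptoms and require intervention/therapy, i.e. are clinically significant".

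Protocol 7.1 defines the endpoints. The efficacy endpoints in 7.1.1 include "Mean change in BCDVA from baseline to Week 8". The only safety endpoint, in 7.1.3, is "Adverse Events (AEs) and Treatment-emergent adverse events (TEAEs), assessed throughout the study".

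Protocol 8.1 lists sight-threatening AESIs and says that they "will be considered equivalent to a SAE and will be reported following the procedures described below for the reporting of a SAE". The first criterion is an AE that causes an acuity loss of more than 30 ETDRS letters (or more than 0.6 logMAR) for over an hour. Another is an AE that, in the investigator's opinion, required medical intervention to prevent permanent loss of sight. The SAE definition in 8.1 also covers important medical events that may need medical or surgical intervention.

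Protocol 8.4.1 requires SAEs to be reported within 24 hours. SAP 6.1 puts SAEs in the overall TEAE summary and provides a listing of serious TEAEs. It mentions no AESI output.

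**The concern.** Two rules in the same safety section give different answers for the same event. An AE that costs an eye more than 30 letters must be handled as an SAE under 8.1. It also concerns a parameter that is a listed endpoint, and 8.4.2 says that end points are not SAEs. A site that works from the exclusion list could record the event as an AE and leave the serious box unticked.

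Safety is part of the primary objective, the study has one arm, and 35 evaluable patients are planned at about five sites. If sites read the two sections differently, the count of serious events depends partly on the reading. An event not flagged as serious could also miss the 24-hour report, which would delay the sponsor's assessment under the 7- and 15-day rules in 8.4.3.

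**Working it through.** The point rests on comparing text, and the plan gives no figure to reproduce.

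**1. Do the two rules overlap?**

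| Event or outcome | Listed endpoint in 7.1? | Status under 8.1 | Status under 8.4.2, read literally |
|---|---|---|---|
| AE causing an acuity loss of more than 30 letters for over an hour | The parameter (BCDVA) is; the AE falls under 7.1.3 | Equivalent to an SAE | Not an SAE |
| AE needing intervention to prevent permanent sight loss | Yes, as an AE under 7.1.3 | Equivalent to an SAE | Not an SAE |
| Important medical event | Yes, as an AE under 7.1.3 | SAE | Not an SAE |
| Central staining unchanged at Week 8, no other event | Yes (non-healing) | Neither criterion met on staining alone | Not an SAE |

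Only the last row is free of conflict, and it is presumably what the bullet was meant to cover.

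As a side check, the acuity threshold is internally consistent. SAP 5.2 equates 15 letters with 0.3 logMAR, so one letter is 0.3/15 = 0.02, and 30 letters are 30 × 0.02 = 0.60 logMAR, as 8.1 states.

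**2. Does any text state precedence?** None found. The AESI rule sends the reader to the SAE reporting procedures that follow it. Those are in section 8.4, which contains the exclusion.

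**3. The test-result bullet.** It has two grammatical readings:

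- The negation governs the whole phrase. Only results that cause no symptoms, need no therapy and are not clinically significant are exempt. This is the conventional rule and the likelier intent.
- The negation governs only the first verb. Results without symptoms that do need therapy are then exempt, which conflicts with the important-medical-event criterion and the AESI intervention criterion. Protocol 2.1 defines Stage 1 NK partly by reduced corneal sensation, so worsening with few symptoms is plausible here.

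**4. What is kept and what could be lost?**

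- Kept: the AE record. The AE definition in 8.1 includes "or the significant worsening of the disease under investigation", 8.2 requires clinically relevant worsening of any protocol parameter to be reported as an AE, and 8.3 collects AEs from consent. If treatment-emergent, the event enters Tables 14.3.1.2 to 14.3.1.4, and 14.3.1.5 if study medication is withdrawn. It also enters Listing 16.2.7.
- At risk: the serious flag, hence the 24-hour report, the SAE count in the overall summary (Table 14.3.1.1) and the serious-TEAE listing (14.3.2).

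**5. Illustration of size.** The documents give no serious ocular event rate, so the event numbers are assumed. Take n = 35 and exact (Clopper-Pearson) 95% intervals:

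- 0 events: 0/35 = 0%. Upper limit = 1 − 0.025^(1/35) = 10.0%.
- 1 event: 1/35 = 2.9%. Lower limit = 1 − 0.975^(1/35) = 0.07%. Upper limit = 97.5th percentile of Beta(2, 34) = 14.9%.
- 2 events: 2/35 = 5.7%, interval 0.7% to 19.2%.

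One unflagged event changes the first of two events, or the only one: in the latter case the reported result moves from 2.9% (0.07% to 14.9%) to 0% (upper limit 10.0%).

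**The case against.** The strongest reply is that the AESI rule is the specific provision and the end-point bullet the generic one, so a careful site would follow 8.1. Protocol 3.2 helps this reading, since it asks for 24-hour reporting of SAEs and of other important AEs specified in section 8. The 7.1.1 endpoints are also percentages, mean changes and a 15-letter gain; an individual acuity loss is not itself named. This stands as far as likelihood goes: non-reporting is a risk and not a certainty. It does not remove the conflict, because neither 3.2 nor 8.1 mentions the exclusion and the exclusion mentions neither.

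A reader might infer more than the documents support:

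- *That 8.4.2 contradicts the AE definition.* It does not. An event can be an AE without being an SAE, and 8.4.2 settles only the second question.
- *That corneal ulcer, persistent defect, melting or perforation are exempted by name.* They appear in the deterioration and discontinuation criteria (3.3 and 6.2), not among the endpoints. The bullet reaches them only indirectly, through the staining endpoints or the AE endpoint. Acuity loss is the more direct example.
- *That the bullet exempts every AE, because AEs are the safety endpoint.* That is its literal effect, but it would empty section 8.4, so no site is likely to read it so. It shows that the bullet cannot stand as worded.
- *That the event would be recorded only as an efficacy failure and vanish from the analysis.* The AE duties and tables in step 4 of the check rule this out.
- *That the test-result bullet plainly exempts clinically significant results.* It is ambiguous, and the conventional meaning is the likelier intent.

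The rows of Table 14.3.1.1 cannot be inspected: the SAP says that mock shells are a separate working document, and its Appendix 2 gives titles only. What can be said is that neither the text of SAP 6.1 nor the list of titles mentions AESIs.

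**Conclusion.** The concern holds in a limited form. The unqualified exclusion in 8.4.2 conflicts with the AESI rule and with the important-medical-event criterion in 8.1, and nothing settles which prevails. The exposure is the serious classification of a sight-threatening event and the reporting and tabulation that follow from it, not the record of the event.

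The rates at n = 35 are illustrative only. They assume one or two serious events and a denominator of 35. The 35 are patients who complete 8 weeks, and earlier dropouts are replaced, while safety is summarized on the FAS, which is everyone dosed. The denominator may therefore exceed 35, and each event would then weigh slightly less. The efficacy analyses are not affected.

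**What to change.** Reconcile Protocol 8.4.2 with 8.1:

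- Delete the end-point bullet, or limit it to efficacy outcomes that meet no SAE or AESI criterion in 8.1.
- State in 8.4.2 that the SAE and AESI criteria in 8.1 prevail over the exclusion list.
- Reword the test-result bullet so that it exempts only results that cause no signs or symptoms, need no intervention and are not clinically significant.
- In SAP 6.1, have the serious-event count include AESIs, so that the summary does not depend on how a site ticked the box.

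The cost is a wording amendment to the protocol, one clarification in the SAP and possibly a few more expedited reports. No dose, visit, assessment or clinical rule changes.

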8.4.3. Reporting Procedure to IRB/IEC and to Regulatory Authorities

SUSAR shall be reported to the Regulatory Authority (FDA and non-US concerned Authority as applicable) by Dompé as soon as possible and in no event later than:

- (a) seven calendar days after becoming aware of the information if the event is fatal or life threatening; to be followed by any relevant information within eight days.
- (b) fifteen calendar days after becoming aware of the information if the event is neither fatal nor life threatening.

Lexitas Pharma Services, Inc shall follow up on safety information and shall report any relevant updated findings as soon as available.

If the results of an investigation show that an adverse drug reaction not initially determined to be reportable is reclassified as reportable, *Dompé* shall report such reaction in a written safety report as soon as possible, but in no event later than 7/15 calendar days after the determination is made.

In addition, each IRB/IEC/Regulatory Authority and Investigator will receive appropriate periodic safety updates as per applicable local requirements and regulations.

In addition to reporting the SAE to Dompé and Lexitas, the Investigator must also comply with the requirements related to the reporting of SAEs to the local IRB which approved the study. The requirements of IRBs vary from one IRB to another; however, as a minimum requirement, the Investigators must promptly report all suspected unexpected serious adverse reactions (SUSAR) to their IRB.

In line with provisions set forth in 21CFR312, Dompé shall notify all participating Investigators in an IND safety report of any suspected adverse reaction that is both serious and unexpected and of potential serious risks, from clinical trials or any other source, as soon as possible, but in no case later than:

- seven calendar days after becoming aware of the information if the event is fatal or life threatening; to be followed by any relevant information within eight days.
- fifteen calendar days after becoming aware of the information if the event is serious but neither fatal nor life threatening.

The Investigators in turn shall notify their local IRB.

Copies of all correspondence relating to reporting of any SUSARs to the local IRB should be maintained in the Investigator's Files.

Dompé shall also notify FDA in an IND safety report of potential serious risks, from clinical trials or any other source, as soon as possible after Dompé determines that the information qualifies for reporting, shall notify of:

- any suspected adverse reaction that is both serious and unexpected. Dompé must report an adverse event as a suspected adverse reaction only if there is evidence to suggest a causal relationship between the drug and the adverse event.
- findings from other studies that suggest a significant risk in humans exposed to the drug. Such a finding would result in a safety-related change in the overall conduct of the clinical investigation.
- findings from animal or in vitro testing that suggest a significant risk in humans exposed to the drug
- increased rate of occurrence of serious suspected adverse reactions.

8.4.4. Periodical Reporting to Regulatory Authorities

Dompé shall be responsible to prepare and submit annual safety reports (Development Safety Update Report – DSUR) to relevant Regulatory Authorities.

8.5. EXPOSURE TO STUDY PRODUCT DURING PREGNANCY

Women of childbearing potential are not excluded from the study if adequate birth control methods are being utilized. Women of childbearing potential are defined as all women physiologically capable of becoming pregnant. Adequate birth control methods are summarized in the protocol's exclusion criteria. Prior to enrolment in the clinical trial, female patients of childbearing potential and their partners must be advised of the importance of avoiding pregnancy during the entire course of the study treatment and for the 30 days after the study treatment period ends and of the potential risks associated with an unintentional pregnancy. During the trial, female patients are to be instructed to contact the Investigator immediately if they suspect they might be pregnant. In the same way, male patients who become aware that the partner might be pregnant, are to be instructed to contact the Investigator immediately.

The Investigator must report every pregnancy on a Pregnancy Report Form as soon as possible (within 24 hours of learning of the pregnancy) to the same contacts specified in Section 8.4.1., even if no AE has occurred, and follow it to term. If, however, the pregnancy is associated with an SAE (e.g., if the mother is hospitalized for dehydration), in addition to the pregnancy report form, a separate SAE report form must be filed as described in Section 8.4.1. with the appropriate serious criterion (e.g., hospitalization) indicated on the SAE report form.

Any pregnancy leads to the immediate exclusion from the trial. Miscarriage, stillbirth, and any malformation/disease must be reported as a SAE.

The pregnant woman (patient or partner) should be followed for pregnancy outcome through delivery or termination of the pregnancy. In any pregnancy that progresses to term, the infant should be followed until 6 months after birth and any congenital abnormalities/birth defects in the infant should be reported as an SAE.

8.6. ADVERSE EVENTS CAUSING TREATMENT DISCONTINUATION

If a patient is withdrawn from the study as a consequence of an AE, this must be recorded and reasoned in the CRF, and the patient must be followed up until the resolution of the AE or as instructed by the medical monitor.

8.7. OVERDOSE

Cases of overdose (accidental or intentional) should be reported in the eDC. Any overdose which results in a serious adverse event is to be reported to Dompé and Lexitas Pharmacovigilance and Dompé Medical Expert, following the same procedure for SAE, within 24 hours from the Investigator's knowledge of its occurrence. This includes reports related to drug intake through different routes (e.g. ingestion) or with suicidal intentions and consequent drug overdose.

An overdose of OXERVATE $^{\text{\tiny TM}}$ 0.002% (20 mcg/mL) cenegermin-bkbj ophthalmic solution is defined as the administration of 50% or more additional drops on any given treatment day.

The Investigator shall provide information about symptoms, corrective treatment, and outcome of overdose. The Medical Expert should be contacted to discuss corrective treatment, if necessary.

This is a single-arm open-label trial with no provisions for masking Study Product.

9. STATISTICS

A general description of the statistical methods used to analyze the efficacy and safety data is outlined below. Specific details will be provided in the Statistical Analysis Plan (SAP).

9.1. SAMPLE SIZE

A sample size of 35 evaluable patients (patients completing 8 weeks of OxervateTM) will achieve a lower limit of 95% confidence interval equal to 40% and 54% when the percentage of subjects who experience epithelial healing is 58% (at 4-week) and 72% (at 8-week), respectively.

The sample size calculation was based on previous trial calculations from NGF0212 (REPARO) and NGF0214 (US trial) that showed statistical superiority in complete healing after 8 weeks of treatment with cenegermin, 72% and 65.5% respectively. Assumption for this target, has been proportion of patients achieving complete healing of staining (grade 1 or less on NEI scale) by week 8.

9.2. PATIENT POPULATION

Screened Population

The Screened Population will consist of all patients who attended Screening, signed the ICF, and were assigned a PID number.

Analysis Sets

Full Analysis Set: consist of all patients who receive at least one dose of study drug.

Full Treated Set: consist of all patients who receive all 8 weeks of treatment.

